### **5.9.1 Discontinuation of Study Therapy after CR**

For subjects who have **overt disease** at any point during study treatment, discontinuation of treatment may be considered if they attain a **confirmed CR** AND have been treated for at least 24 weeks with pembrolizumab and had at least two treatments with pembrolizumab beyond the date when the initial CR was declared. Subjects who then experience radiographic disease progression may be eligible for up to one year of additional treatment with pembrolizumab via the Second Course Phase at the discretion of the investigator if no cancer treatment was administered since the last dose of pembrolizumab, the subject meets the safety parameters listed in the Inclusion/Exclusion criteria, and the trial is open. Subjects will resume therapy at the same dose and schedule at the time of initial discontinuation. Additional details are provided in Section 7.1.5.5.

### **5.10 Subject Replacement Strategy**

Patients who receive 0, or only 1 dose only will be replaced due to inadequate treatment exposure. An intention to treat analysis will be performed as a secondary analysis, but for the primary analysis only patients with adequate treatment exposure to 2 or more doses of pembrolizumab will be included.

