**Table 6: Imaging and Treatment After First Radiologic Evidence of Progressive Disease**

	Clinically Stable		Clinically Unstable	
	Imaging	Treatment	Imaging	Treatment
First radiologic evidence of PD	Repeat imaging at $\geq 4$ weeks to confirm PD	May continue study treatment at the investigator's discretion while awaiting confirmatory scan	Repeat imaging at $\geq 4$ weeks to confirm PD if possible	Discontinue treatment
Repeat scan confirms PD	No additional imaging required	Discontinue treatment	No additional imaging required	N/A
Repeat scan shows SD, PR, or CR	Continue regularly scheduled imaging assessments every 9 weeks	Continue study treatment at the investigator's discretion	Continue regularly scheduled imaging assessments every 9 weeks	May restart study treatment if condition has improved and/or clinically stable per investigator's discretion

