***If clinically indicated tissue from a biopsy will also be banked using the UCCCC# 8980 banking protocol.***

**2. -- 2 Purple top tubes, blood volume, processing etc will follow HTRC SOPs**

**3. – PAXgene tube, blood volume, processing etc will follow HTRC SOPs**

**\* Treatment cycle length = 21 days**

**\*\* After cycle 8, as clinically appropriate ECOG performance status, physical exam, and adverse event recording interval may be increased to every other cycle (=every 6 weeks).**

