### **7.1.2.5 Tumor Imaging and Assessment of Disease**

Tumor imaging will be performed as outline in the flowchart under Section 6, typically every 8-16 weeks or as clinically indicated.

Radiologic recurrence/progression of disease should be confirmed 4-8 weeks after the initial scan and patients can continued treatment until confirmation if clinically stable and no other immediate reason for discontinuation is present.

Whenever possible clinical progression should be confirmed radiologically.

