#### **Primary Outcome: Response rate**

Clinical and pathologic response rates will be determined and 90% confidence intervals obtained using the exact binomial distribution.

A Simon's two-stage design (Simon, 1989) will be used – using the Minimax variant - for both cohorts. The null hypothesis that the true response rate is 3% [ $p_0$ ] (*assuming poor efficacy of e.g. pembrolizumab treatment in patients, who have failed prior PD-1/PD-L1 therapy*) will be tested against a one-sided alternative. In the first stage, 10 [ $n_1$ ] patients will be accrued. If there are no responses [ $r_1$ ] in these 10 [ $n_1$ ] patients, the study will be stopped.

Otherwise, 5 additional patients will be accrued for a total of 15 [ $n$ ] patients. The null hypothesis will be rejected if 2 or more responses are observed in 15 patients. This design yields a type I error rate of 0.0667 and 80% power when the true response rate is 20%.

A response rate of 20% would be considered clinically meaningful for HNC in the absence of alternative treatment options in the 2nd/3rd line setting (after PD-1/PD-L1 failure) and further development of pembrolizumab + epacadostat would proceed.

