## 8.2 Sample Size

Sample size for each cohort is up to 15 patients (total of up to 30 patients).

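### The primary response analysis drops and replaces treated patients who receive only one pembrolizumab dose, which is expected to bias the response rate upward and leaves the Simon denominator undefined

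*Combined protocol and SAP*

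**What the plan says.** Section 5.10 (Subject Replacement Strategy) sets the replacement rule: "Patients who receive 0, or only 1 dose only will be replaced due to inadequate treatment exposure". It then defines the main analysis set: "for the primary analysis only patients with adequate treatment exposure to 2 or more doses of pembrolizumab will be included". An intention-to-treat analysis is planned, but as a secondary one. The rule makes no exception for early death, progression or toxicity.

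Section 8.1 applies a Simon two-stage design to each cohort. Ten patients are accrued, and the cohort stops if none responds. Otherwise "5 additional patients will be accrued for a total of 15", and "The null hypothesis will be rejected if 2 or more responses are observed in 15 patients". The null rate is 3%, the alternative 20%, the stated type I error 0.0667 and the stated power 80%. Section 8.2 caps each cohort at 15 patients and the trial at 30. Neither section refers to 5.10 or mentions replacements.

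On timing, the flow chart footnote in section 6.1 gives "Treatment cycle length = 21 days". Section 7.1.2.5 puts tumor imaging at "typically every 8-16 weeks or as clinically indicated", and Table 6 has "Continue regularly scheduled imaging assessments every 9 weeks". The imaging row of the flow chart is not readable in the text supplied.

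**The concern.** Whether a treated patient enters the primary analysis depends on something that happens after treatment starts, namely reaching dose 2 at about week 3. A patient who stops before then has normally not had a routine response scan. Section 4.2.4.1 describes a population with median survival of 6 months or less, and Cohort 1 enters with progressive disease. The one-dose group is therefore expected to consist mostly of early deaths, clinical progressions, toxicity stops and withdrawals, who respond less often than those who continue. Removing and replacing them raises the expected response rate.

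A one-dose responder is possible, because patients who stop for reasons other than progression stay in imaging follow-up (sections 5.9 and 7.2.8.5). Section 5.10 would drop that patient too. Replacing patients who were never treated is not at issue.

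A second problem does not depend on how many such patients there are. The go/no-go rule turns on one response in 10 and two in 15, so it needs a defined denominator. The plan does not say whether the 10 and 15 are treated patients or the selected, replaced set. It also does not say which population has the 3% and 20% rates, so the stated type I error and power have no named population.

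**Working it through.** **Inputs from the documents.** n1 = 10, stop at 0 responses; n = 15, reject at 2 or more; p0 = 3%, p1 = 20% (section 8.1). Cap of 15 per cohort (section 8.2).

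**Input assumed.** q, the share of treated patients who receive only one dose. The documents do not give it, so 5% to 25% is used. It may be lower in Cohort 2, which requires ongoing stable disease.

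**Formula.** For response rate p in the patients counted:

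P(reject) = P(X15 ≥ 2) − (1−p)^10 × P(X5 ≥ 2),

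where X15 and X5 are binomial with 15 and 5 patients. The subtracted term is the chance of stopping at stage 1 when the other five patients would have met the final rule. P(pass stage 1) = 1 − (1−p)^10.

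**The plan's own figures.**
- p = 0.03: 0.07297 − 0.73742 × 0.00847 = 0.0667. P(pass stage 1) = 0.2626.
- p = 0.20: 0.83287 − 0.10737 × 0.26272 = 0.8047.

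Both agree with section 8.1.

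**Reading A: 3% and 20% are all-treated rates, and 5.10 governs the counts.** If no one-dose patient responds, the analysed rate is p/(1−q). For example, at q = 10%, 0.03/0.90 = 0.0333. If 1% of one-dose patients respond, the analysed null rate is (0.03 − 0.01q)/(1−q).

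| q | Analysed rate, true 3% | P(reject) | P(pass stage 1) | P(reject) if 1% of one-dose patients respond | Analysed rate, true 20% | P(reject) |
|---|---|---|---|---|---|---|
| 0 | 3.00% | 0.0667 | 0.2626 | 0.0667 | 20.0% | 0.805 |
| 5% | 3.16% | 0.0730 | 0.2745 | 0.0709 | 21.1% | 0.829 |
| 10% | 3.33% | 0.0802 | 0.2875 | 0.0756 | 22.2% | 0.853 |
| 20% | 3.75% | 0.0980 | 0.3176 | 0.0872 | 25.0% | 0.899 |
| 25% | 4.00% | 0.1093 | 0.3352 | 0.0944 | 26.7% | 0.920 |

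If one-dose patients respond as often as the rest, there is no inflation.

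**Reading B: 3% and 20% are rates in the two-or-more-dose set.** The stated 0.0667 and 80% then hold for that set. With one-dose patients as non-responders, the all-treated rate is p(1−q). If all treated patients were counted in the 10 and 15:

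| q | All-treated null rate | Type I error | All-treated alternative rate | Power |
|---|---|---|---|---|
| 5% | 2.85% | 0.061 | 19% | 77.9% |
| 10% | 2.70% | 0.055 | 18% | 75.1% |
| 20% | 2.40% | 0.045 | 16% | 68.6% |
| 25% | 2.25% | 0.040 | 15% | 64.9% |

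**Patients needed.** A cohort that goes to full size with replacement needs on average 15/(1−q) treated patients to reach fifteen with two or more doses: 15.8, 16.7, 18.8 or 20.0 for q = 5%, 10%, 20% or 25%. Section 8.2 allows 15.

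**The case against.** The strongest objection is that the inflated type I error is conditional twice over. It requires 5.10 to govern the Simon counts, and it requires 3% and 20% to be all-treated rates; the documents state neither. It would be natural to read the design rates as describing the set on which the primary analysis is run. In that case nothing stated in section 8.1 is wrong. This stands as a limit on the type I error claim. It does not remove the bias in the primary estimate relative to all treated patients, and it leaves the loss of all-treated power under that reading undisclosed.

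The size also rests on an assumed q, and some provisions point to the low end. Entry requires ECOG 0 or 1. A first radiologic progression need not end treatment in a clinically stable patient (section 5.7.3). Many toxicities lead to a hold with up to 12 weeks to resolve (Table 3), so a held patient may still receive dose 2. At q = 5% the shift, from 0.0667 to 0.073, is small beside the imprecision of 15 patients. That is fair, and the size should be read as a range.

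The make-up of the one-dose group is inferred. Lower response is plausible for early death or progression, and less certain for stops due to toxicity or withdrawn consent.

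Finally, the rule is prespecified and the intention-to-treat result will be reported, so readers can see both estimates. But that analysis is labelled secondary, and nothing in the plan gives it a role in the stop or reject decision.

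**Conclusion.** The concern holds and should be fixed. The primary analysis selects patients on a post-treatment event linked to outcome, so the reported response rate is expected to exceed the all-treated rate. The direction is well supported by the timing of dose 2 and of imaging. The size is not fixed by the documents.

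For q of 5% to 25% with no one-dose responders, a true 20% rate is expected to appear as 21.1% to 26.7%. If 5.10 governs the Simon counts and 3% is an all-treated rate, type I error is 0.073 to 0.109 (0.071 to 0.094 if 1% of one-dose patients respond). If the design rates belong to the two-or-more-dose set, type I error is not inflated, but all-treated power is 78% to 65%. Under either reading, the plan must name the population for its decision rule and reconcile replacement with the cap of 15.

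**What to change.** Amend sections 5.10, 8.1 and 8.2 to define one primary set for both Simon stages: all patients who receive at least one dose of study treatment, counted in enrolment order (the first 10, then the first 15 in each cohort).

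- Count patients without an evaluable post-baseline scan as non-responders.
- Count a one-dose patient with a RECIST 1.1 response as a responder.
- Replace only never-treated patients.
- State that 3% and 20% refer to all treated patients.
- Keep intention to treat as a secondary analysis and report the two-or-more-dose set as a sensitivity analysis.

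The cost is wording only. No extra patients are needed, because one-dose patients are no longer replaced. If 3% and 20% are all-treated rates, the 0.0667 and 80% are kept. If they were meant for the two-or-more-dose set, all-treated type I error and power must be restated as in the second table, at a stated value of q.

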### **5.11 Clinical Criteria for Early Trial Termination**

Early trial termination at a participating site will be the result of the criteria specified below:

1. Quality or quantity of data recording is inaccurate or incomplete
2. Poor adherence to protocol and regulatory requirements
3. Incidence or severity of adverse drug reaction in this or other studies indicates a potential health hazard to subjects
4. Plans to modify or discontinue the development of the study drug

In the event of Merck/Incyte decision to no longer supply study drug, ample notification will be provided so that appropriate adjustments to subject treatment can be made.

## 6.0 TRIAL FLOW CHART

### 6.1 Study Flow Chart

Trial Period:	Screening Phase		Treatment Cycles *								End of Treatment (D/C)	Post-Treatment			
	Treatment Cycle/Title:	Pre-screening (Visit 1)	Main Study Screening (Visit 2)	1	2	3	4	To be repeated beyond 8 cycles **				Safety Follow-up	Follow Up Visits	Survival Follow-Up	
Scheduling Window (Days):		-28 to -1		± 3	± 3	± 3	± 3	± 3	± 3	± 3	± 3	At time of D/C	30 days post D/C	Every 8 weeks post D/C	Every 12 weeks
Administrative Procedures															
Informed Consent	X														
Inclusion/Exclusion Criteria	X	X													
Demographics and Medical History	X	X													
Prior and Concomitant Medication Review	X	X	X	X	X	X	X	X	X	X	X	X			
Trial Treatment Administration			X	X	X	X	X	X	X	X	X				
Post-study anticancer therapy status												X			
Survival Status												X	X	X	X
Clinical Procedures/Assessments															
Epacadostat administration (daily po)			X	X	X	X	X	X	X	X	X				
Pembrolizumab administration (iv q3 weeks)			X	X	X	X	X	X	X	X	X				
Review Adverse Events			X	X	X	X	X	X**	X	X**	X				
Full Physical Examination		X	X	X	X	X	X	X**	X	X**	X	X	X	X	
Vital Signs and Weight		X	X	X	X	X	X	X	X	X	X	X	X	X	
ECOG Performance Status		X	X	X	X	X	X	X**	X	X**	X	X	X	X	

Trial Period:	Screening Phase		Treatment Cycles*								End of Treatment	Post-Treatment			
	Treatment Cycle/Title:	Pre-screening (Visit 1)	Main Study Screening (Visit 2)	1	2	3	4	To be repeated beyond 8 cycles**				Discontinuation (D/C)	Safety Follow-up	Follow Up Visits	Survival Follow-Up
							5	6	7	8					
Scheduling Window (Days):		-28 to -1		± 3	± 3	± 3	± 3	± 3	± 3	± 3	± 3	At time of D/C	30 days post D/C	Every 8 weeks post D/C	Every 12 weeks
feasible															
Correlative Studies Blood Collection including a) germline DNA collection and b) PAXgene tube for RNA		X 		X 											

**1. The fresh biopsy/FNA requirement can be waived under extenuating circumstances after approval by the PI ([name]) e.g such a procedure is not safe or technically feasible.**

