#### **5.9 Subject Withdrawal/Discontinuation Criteria**

Subjects may withdraw consent at any time for any reason or be dropped from the trial at the discretion of the investigator should any untoward effect occur. In addition, a subject may be withdrawn by the investigator or the Sponsor if enrollment into the trial is inappropriate, the trial plan is violated, or for administrative and/or other safety reasons. Specific details regarding discontinuation or withdrawal are provided in Section 7.1.4 – Other Procedures.

A subject must be discontinued from the trial for any of the following reasons:

- The subject or legal representative (such as a parent or legal guardian) withdraws consent.
- Confirmed radiographic disease progression (=2nd scan within 4-8 weeks)

*Note:* For unconfirmed radiographic disease progression, please see Section 5.7.3

*Note:* A subject may be granted an exception to continue on treatment with confirmed radiographic progression if clinically stable or clinically improved, please see Section 5.7.3

- Unacceptable adverse experiences as described in Section 5.2.1.2
- Intercurrent illness that prevents further administration of treatment
- Investigator's decision to withdraw the subject
- The subject has a confirmed positive serum pregnancy test
- Noncompliance with trial treatment or procedure requirements
- The subject is lost to follow-up
- Completed 12 months of uninterrupted treatment with pembrolizumab or 18 administrations of study medication, whichever is later.

- Administrative reasons

The End of Treatment and Follow-up visit procedures are listed in Section 6 (Protocol Flow Chart) and Section 7.1.5 (Visit Requirements). After the end of treatment, each subject will be followed for 30 days for adverse event monitoring (serious adverse events will be collected for 90 days after the end of treatment as described in Section 7.2.3.1). Subjects who discontinue for reasons other than progressive disease will have post-treatment follow-up for disease status until disease progression, initiating a non-study cancer treatment, withdrawing consent or becoming lost to follow-up. After documented disease progression each subject will be followed by telephone for overall survival until death, withdrawal of consent, the end of the study, or 2 years beyond the last administration of study drug, whichever occurs first.

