### **7.1.2 Clinical Procedures/Assessments**

#### **7.1.2.1 Adverse Event (AE) Monitoring**

The investigator or qualified designee will assess each subject to evaluate for potential new or worsening AEs as specified in the Trial Flow Chart and more frequently if clinically indicated. Adverse experiences will be graded and recorded throughout the study and during the follow-up period according to NCI CTCAE Version 4.0. Toxicities will be characterized in terms regarding seriousness, causality, toxicity grading, and action taken with regard to trial treatment.

Please refer to section 7.2 for detailed information regarding the assessment and recording of AEs.

Safety assessments will consist of monitoring and recording all adverse events and serious adverse events, the regular monitoring of hematology, blood chemistry and urine values, regular measurement of vital signs and the performance of physical examinations.

These assessments should be performed within  $\pm 7$  days of the scheduled day of assessment except for adverse events that will be evaluated continuously through the study. Safety and tolerability will be assessed according to the NIH/NCI CTC [http://evs.nci.nih.gov/ftp1/CTCAE/CTCAE\\_4.03\\_2010-06-14\\_QuickReference\\_5x7.pdf](http://evs.nci.nih.gov/ftp1/CTCAE/CTCAE_4.03_2010-06-14_QuickReference_5x7.pdf)

Patients whose treatment is interrupted or permanently discontinued due to an adverse event or abnormal laboratory value suspected to be related to treatment must be followed at least weekly until the adverse event or abnormal laboratory resolves or returns to grade 1. If a patient requires a dose delay of >16 weeks from the intended day of the next scheduled dose, then the patient must be discontinued from the study.

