### **7.2.8.4 Post-Treatment Visits**

#### **7.1.5.4.1 Safety Follow-Up Visit**

The mandatory Safety Follow-Up Visit should be conducted approximately 30 days after the last dose of trial treatment or before the initiation of a new anti-cancer treatment, whichever comes first. All AEs that occur prior to the Safety Follow-Up Visit should be recorded. Subjects with an AE of Grade > 1 will be followed until the resolution of the AE to Grade 0-1 or until the beginning of a new anti-neoplastic therapy, whichever occurs first. SAEs that occur within 90 days of the end of treatment or before initiation of a new anti-cancer treatment should also be followed and recorded. Subjects who are eligible for retreatment with pembrolizumab (as described in Section 7.1.5.5) may have up to two safety follow-up visits, one after the Treatment Period and one after the Second Course Phase.

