#### **7.2.8.5.1 Survival Follow-up**

Once a subject experiences confirmed disease progression or starts a new anti-cancer therapy, the subject moves into the survival follow-up phase and should be contacted by telephone approximately every 12 to 16 weeks to assess for survival status until death, withdrawal of consent, or the end of the study, whichever occurs first OR at most 2 years out from the last patient receiving pembrolizumab.

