### 7.3 Assessing and Recording Adverse Events

An adverse event is defined as any untoward medical occurrence in a patient or clinical investigation subject administered a pharmaceutical product and which does not necessarily have to have a causal relationship with this treatment. An adverse event can therefore be any unfavorable and unintended sign (including an abnormal laboratory finding, for example),

Protocol #: UC IRB17-1539

Version Date: 1/23/2018

symptom, or disease temporally associated with the use of a medicinal product or protocol-specified procedure, whether or not considered related to the medicinal product or protocol-specified procedure. Any worsening (i.e., any clinically significant adverse change in frequency and/or intensity) of a preexisting condition that is temporally associated with the use of the Merck/Incyte products, is also an adverse event.

Changes resulting from normal growth and development that do not vary significantly in frequency or severity from expected levels are not to be considered adverse events. Examples of this may include, but are not limited to, teething, typical crying in infants and children and onset of menses or menopause occurring at a physiologically appropriate time.

Merck/Incyte product includes any pharmaceutical product, biological product, device, diagnostic agent or protocol-specified procedure, whether investigational (including placebo or active comparator medication) or marketed, manufactured by, licensed by, provided by or distributed by Merck/Incyte for human use.

Adverse events may occur during the course of treatment in clinical trials or within the follow-up period specified by the protocol, or prescribed in clinical practice, from overdose (whether accidental or intentional), from abuse and from withdrawal.

Progression of the cancer under study is not considered an adverse event unless it is considered to be drug related by the investigator.

All adverse events will be recorded from the time of first study drug administration through 90 days following cessation of treatment or if a subject initiates new anticancer therapy, whichever is earlier and at each examination on the Adverse Event case report forms/worksheets. The reporting timeframe for adverse events meeting any serious criteria is described in section 7.2.3.1.

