### **7.3.3 Immediate Reporting of Adverse Events to Incyte and Merck**

#### **7.3.3.1 Serious Adverse Events**

A serious adverse event is any adverse event occurring at any dose or during any use of Merck/Incyte products that:

- Results in death;
- Is life threatening;
- Results in persistent or significant disability/incapacity;
- Results in or prolongs an existing inpatient hospitalization;
- Is a congenital anomaly/birth defect;
- Is a new cancer (that is not a condition of the study);

Protocol #: UC IRB17-1539

Version Date: 1/23/2018

- Is associated with an overdose;
- Is an other important medical event

Refer to Table 8 for additional details regarding each of the above criteria.

Any serious adverse event, or follow up to a serious adverse event, including death due to any cause other than progression of the cancer under study that occurs to any subject from the time of first dose of study drug through 90 days following cessation of treatment, or the initiation of new anti-cancer therapy, whichever is earlier, whether or not related to Merck/Incyte products, must be reported within 24 hours to the Sponsor and within 2 working days to Incyte/Merck Global Safety as described in section 10.7.

Non-serious Events of Clinical Interest will be forwarded to Incyte / Merck Global Safety and will be handled in the same manner as SAEs.

Additionally, any serious adverse event, considered by an investigator who is a qualified physician to be related to Merck/Incyte products that is brought to the attention of the investigator at any time outside of the time period specified in the previous paragraph also must be reported immediately to the Sponsor and to Merck /Incyte as described in section 10.7.

This study will be conducted under an IND held by [name] at the University of Chicago. Annual Progress Reports will be submitted as required by FDA. Additionally the IND holder will submit a copy of these reports to Incyte/Merck & Co., Inc. (Attn: Worldwide Product Safety; [contact]) at the time of submission to FDA.

All subjects with serious adverse events must be followed up for outcome.

The investigator must assess and record the relationship of each SAE to the specific study drug, and report this as described in section 10.7. The original copy of the SAE Report and the fax confirmation sheet must be kept at the study site.

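### After the day-30 Safety Follow-Up Visit, patients who stopped for confirmed progression and have started no new therapy have no scheduled SAE enquiry to day 90, and the flow chart marks no AE review after treatment

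*Combined protocol and SAP*

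**What the plan says.** **The schedule.** Section 7.1.2.1 has AEs assessed "as specified in the Trial Flow Chart and more frequently if clinically indicated", and 7.2.8 refers to the same chart for visit requirements. In 6.1 the row "Review Adverse Events" carries nine marks, in the same columns as drug administration, and is blank afterwards. Physical examination, vital signs and ECOG status are marked in post-treatment columns.

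**The windows.** Section 5.9 follows patients for 30 days for AEs and adds that "serious adverse events will be collected for 90 days after the end of treatment". Section 7.3 is wider: "All adverse events will be recorded from the time of first study drug administration through 90 days following cessation of treatment", or until new anticancer therapy if earlier. Section 7.3.3.1 requires SAEs to be reported "from the time of first dose of study drug through 90 days following cessation of treatment", with the same early cut-off.

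**The contacts.** The Safety Follow-Up Visit (under 7.2.8.4) is mandatory at about day 30, or before new anticancer treatment if that comes first: "All AEs that occur prior to the Safety Follow-Up Visit should be recorded". Imaging follow-up (7.2.8.5; in the chart "Every 8 weeks post D/C") is for patients who stopped for a reason other than progression. After confirmed progression or new therapy, patients "should be contacted by telephone approximately every 12 to 16 weeks to assess for survival status" (7.2.8.5.1). The chart gives 12 weeks for survival follow-up.

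**The concern.** The plan sets a duty to collect SAEs to day 90 but, for one group, provides no occasion on which anyone asks. Without a scheduled question, an SAE between days 31 and 90 reaches the database only if the patient, the family or another clinician volunteers it, or if site staff happen to see it.

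That matters for three reasons. Safety is a secondary objective with a stated hypothesis of tolerability (3.2). Section 8.1 will report toxicity incidence rates. Sections 5.3 and 5.3.2 both warn that immune-related events can appear months after dosing has ended. Any loss would run one way, towards a more favourable toxicity table.

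**Working it through.** The plan states no figure to reproduce. The check reads the chart row, follows the text, and counts days.

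**1. The chart row.** I counted cells after the row label, 15 per row.

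| Row (6.1) | Last marked cell |
|---|---|
| Drug administration | 11 |
| AE review | 11 |
| Concomitant medication | 12 |
| Physical examination, vital signs, ECOG | 14 |
| Survival status | 15 |

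The columns are out of line in the text available: there are nine treatment marks against eight cycle columns. As printed, the scheduling-window line puts discontinuation in cell 12 and the 30-day visit in cell 13. If the marks sit one cell to the left of their headings, discontinuation is cell 11 and the 30-day visit is cell 12. Under either reading the AE row ends before the 30-day visit, while the examination rows continue beyond treatment.

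**2. Contacts after treatment stops, by reason for stopping.**
- *Any reason:* Safety Follow-Up Visit at about day 30, with AEs recorded up to it (7.2.8.4).
- *Not progression:* imaging follow-up from 8 weeks, 8 × 7 = day 56, inside the 90 days.
- *Confirmed progression:* telephone call for survival status only (7.2.8.5.1).

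**3. Days without a scheduled AE or SAE enquiry.** Uncovered days = 90 − day of last enquiry.
- Chart alone, last enquiry no later than discontinuation: 90 − 0 = 90 days.
- Crediting the day-30 visit: 90 − 30 = 60 days; 60/90 = 67%.

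**4. Effect of new therapy.** Collection ends when new anticancer therapy starts, on day *d*. The gap is then min(90, *d*) − 30, or zero if *d* is 30 or less. Illustrative values, not given in the documents: *d* = 45 leaves 15 days and *d* = 60 leaves 30 days. Only patients with no new therapy by day 90 have the full 60.

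**5. When the survival call falls.** The documents do not say from which day the interval runs.
- From discontinuation: 12 × 7 = day 84; 16 × 7 = day 112.
- From the Safety visit: 30 + 84 = day 114; 30 + 112 = day 142.

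At most one call falls inside the window, and its stated purpose is survival.

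**6. Effect of the conflicting AE windows.** With the 30 days in 5.9, the Safety visit covers non-serious AEs (30 − 30 = 0 days uncovered) and the 60-day gap concerns SAEs only. With the 90 days in 7.3, it concerns all AEs. The SAE window is 90 days in 5.9, 7.2.8.4 and 7.3.3.1.

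**7. Scale, not an estimate.** With 30 patients (8.2), one patient whose late SAE is missed moves an incidence rate by 1/30 = 3.3 percentage points; two move it by 2/30 = 6.7.

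**The case against.** The case for the plan is substantial.

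- A reader of the chart might infer that progressing patients have nothing but survival calls once treatment stops, or that AEs are not collected after treatment at all. The documents do not support either reading. The Safety visit has no exception for progression, and 7.1.1.5.3 requires it before any new anticancer therapy begun within 30 days. AEs above Grade 1 are followed until they resolve to Grade 0-1 or new therapy begins.
- Section 7.1.2.1 requires AE recording throughout follow-up, and at least weekly follow-up when treatment stops for a suspected related event. Section 7.3 ties recording to each examination, and examinations are marked after treatment. The blank cells at the Safety and Follow-Up Visit columns are therefore a mismatch between chart and text, not absent ascertainment at those visits.
- Related SAEs remain reportable outside the window (7.3.3.1), and deaths are picked up through survival status.
- Some patients who stop at first radiologic progression have a repeat scan (5.7.3, Table 6), which is a further contact.
- Toxicity is summarised descriptively in at most 30 patients.

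All of this stands, and it narrows the point. It does not close it. The recording duties name no contact in days 31 to 90 for a patient with confirmed progression. The weekly follow-up concerns patients whose treatment was interrupted or stopped for a suspected related event or laboratory abnormality. The repeat scan carries no stated AE question.

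**Conclusion.** The point holds in a limited form. The chart omits an AE-review mark at a visit where the text requires AEs to be recorded. Separately, patients who stopped for confirmed progression and have started no new anticancer therapy have no scheduled SAE enquiry for up to 60 of the 90 days (67%). The same applies to non-serious AEs only if 7.3 prevails over 5.9.

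This rests on three assumptions: the Safety visit takes place at about day 30, the survival call is confined to its stated purpose, and the blank cells are blank in the typeset chart.

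It would be too strong to apply the 67% to every patient who progresses, because collection ends at new therapy and the share who start it by day 90 is not given. It would also be too strong to say that late toxicity *will* be under-counted by a known amount. Late SAEs may be under-counted; the documents give no basis for saying by how many. The change is worth making because it is cheap and protects a secondary endpoint.

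**What to change.** 1. Check the AE-review row in 6.1 against the typeset table. If the cells are blank there, mark it at the Safety Follow-Up and Follow-Up Visit columns, so that the chart agrees with 7.2.8.4.
2. In 6.1 and 7.2.8.5.1, time the first post-progression call at about day 90 after treatment ends, and state that the interval is counted from that date. Add one question on SAEs (and AEs, if the longer window is kept) covering the time since the Safety visit, or up to the start of new anticancer therapy.
3. Reconcile the 30-day AE window in 5.9 with the 90-day window in 7.3, so that staff know what the call must cover.

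The cost is a few chart marks, a sentence or two of text, and one added question in a call that is already planned. The toxicity table may look slightly less favourable. No efficacy analysis or sample size changes.
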